6.6. Interim Analyses and Data Monitoring

6.6.1. Interim Safety Analyses

Interim safety data will be available electronically in real time. No formal interim safety analyses are planned.

6.6.2. Interim Efficacy Review

An interim efficacy analysis will be conducted after approximately 33% of total information has been reached. The information fraction at an interim analysis will be computed as $t = r/723$ where r is the number of recoveries by the time of the data freeze date for the interim analysis. The Lan-DeMets spending function analog of the O'Brien-Fleming boundary will be used to monitor the primary endpoint using an overall two-sided type-I error rate of 0.05. Specifically, two one sided boundaries are constructed at level 0.025 using the spending function

$$\alpha^*(t) = 2[1 - \Phi\{2.241/t^{\frac{1}{2}}\}],$$

where Φ is the standard normal distribution function. Lan-DeMets software from the University of Wisconsin, now available in the R package 'lbound', will be used to calculate boundaries.

Conditional power will be presented as an additional guide to the DSMB. Conditional power allows computation of the probability of obtaining a statistically significant result by the end of the trial given the data accumulated thus far, incorporating and assuming a hypothesized treatment effect (e.g., the treatment effect assumed for sample size determination) thereafter. If conditional power is less than 20% under the original trial assumptions, consideration should be given to stopping the trial.

The unblinded statistical team will prepare these closed session reports for DSMB review and recommendations. Analyses will be presented with blinded codes for treatment arms to protect against the possibility that the DSMB report may fall into the wrong hands. A DSMB Charter will further describe procedures and membership. An additional document on statistical issues related to monitoring may be provided to the DSMB prior to interim analyses.

6.7. Multicenter Studies

Data will be pooled across all clinical sites. Secondary analyses of the primary outcome will account for site via stratification by geographic region as noted in Section 6.4.

A sensitivity analysis of the primary outcome will be performed to assess the impact of individual sites on the observed treatment effect. Letting M be the total number of sites, the primary analysis will be repeated by excluding a single clinical site and performing the analyses on the remaining $M-1$ sites. This process will be repeated so that estimates are generated for each of the $M-1$ subset datasets. Presentations from these analyses are described in Section 8.1.2.

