4.2. Selection of Study Population

Male and non-pregnant female adults ≥ 18 years of age or older with COVID-19 and who meet all eligibility criteria will be enrolled at up to approximately 100 clinical trial sites globally. The target population should reflect the community at large.

See Section 5.1 and 5.2 of Appendix B of the study protocol for the full list of inclusion and exclusion criteria.

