4.2.3. Method of Assigning Subjects to Treatment Groups (Randomization)

Enrollment and randomization of subjects is done online using the enrollment module of Advantage eClinical[®].

Eligible subjects will be randomized and assigned in a 1:1 ratio to either baricitinib + remdesivir or remdesivir, with stratification by site and disease severity by ordinal scale (Moderate disease [4 or 5 on the ordinal scale] or Severe disease [6 or 7 on the ordinal scale]). The randomization is based on a variable blocked scheme to provide an approximately balanced allocation to the treatment groups during the study. If arms are added or removed later in the study, randomization will continue in an equal allocation manner.

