6.4. Covariates and Subgroups

Subgroup analyses for the main efficacy outcomes (i.e. the primary and key secondary analyses) will evaluate the treatment effect across the following subgroups:

- Geographic region:
 - US sites; Non-US sites
 - North American sites; Asian sites; European sites
- Duration of symptoms prior to enrollment
 - Quartiles
 - ≤ 10 days; > 10 days
 - \leq Median; $>$ Median
- Race (White; Black/African American; Asian; Other)
- Comorbidities
 - None; Any
 - None, One, Two or more
 - Obese; Non-Obese
- Age (<40 ; 40-64; 65 and older),
- Sex (Female; Male),
- Severity of disease
 - Randomization stratification: Moderate (ordinal 4/5); Severe (ordinal 6/7).
 - Actual disease severity at baseline: Moderate (ordinal 4/5); Severe (ordinal 6/7)
Note these analyses will only be performed if at least one subject is erroneously randomized into the incorrect disease severity stratum.
 - Baseline ordinal scale category: 4; 5; 6; 7

Additionally, main analyses of all secondary efficacy outcomes will evaluate the treatment effect across the following subgroups:

- Duration of symptoms prior to enrollment (\leq Median; $>$ Median)
- Severity of disease

- Randomization stratification: Moderate (ordinal 4/5); Severe (ordinal 6/7).
- Actual disease severity at baseline: Moderate (ordinal 4/5); Severe (ordinal 6/7)

Note these analyses will only be performed if at least one subject is erroneously randomized into the incorrect disease severity stratum.

- Baseline ordinal scale category: 4; 5; 6; 7

There will also be a sensitivity analysis of the primary, key secondary, and mortality outcomes to evaluate the effect of concomitant therapy including experimental treatment and off-label use of marketed medications that are intended as treatment for COVID-19 and are given to patient prior to and during the study. A blinded review of the concomitant medication data will be performed by the medical monitor to identify medications that fall into any of the following categories of “Medications of Interest”:

- Antivirals
 - Protease inhibitors
 - Polymerase inhibitors
- Potential Treatments for COVID-19
 - Hydroxychloroquine/Chloroquine
 - Other
- Corticosteroids
- Other anti-inflammatory drugs
 - Monoclonal Antibodies Targeting Cytokines
 - Other Biologic Therapies

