8. EFFICACY EVALUATION

8.1. Primary Efficacy Analysis

8.1.1. Primary Analyses

The primary analysis uses the stratified log rank test to compare treatment to control through Day 29 with respect to time to recovery, as defined in Section 3.3. Stratification is based on moderate versus severe disease at baseline. As noted in Section 3.3, all deaths within 29 days will be considered censored at Day 29 with respect to time to recovery. Conceptually, a death corresponds to an infinite time to recovery, but censoring at any time greater than or equal to Day 29 gives the same answer as censoring at Day 29; both correspond to giving deaths the worst rank.

Let MM and S denote the Moderate and Severe subgroups, respectively. The z-score associated with the stratified log rank test is

$$Z = \frac{\sum_{MM}(O_i - E_i) + \sum_S(O_i - E_i)}{\sqrt{\sum_{MM} V_i + \sum_S V_i}}$$

The sums are over recovery times t_i in the moderate and severe subgroups, O_i is the number of treatment arm participants recovering at time t_i , and E_i and V_i are the null expected value and variance of the number of treatment recoveries calculated using the hypergeometric distribution. Specifically, if n_{Ti} and n_{Ci} denote the numbers of patients 'at risk' in the two arms in a given stratum at t_i , and r_i is the total number of recoveries at t_i , then $E_i = r_i n_{Ti} / (n_{Ti} + n_{Ci})$ and $V_i = r_i (n_i - r_i) n_{Ti} n_{Ci} / [n_i^2 (n_i - 1)]$, where $n_i = n_{Ti} + n_{Ci}$. The O_i , E_i , and V_i are computed separately within the moderate and severe strata.

As noted in Section 6.6.2, to maintain an overall two-sided type-I error rate of 0.05, the Lan-DeMets spending function analog of the O'Brien-Fleming boundary will be used to derive the cumulative error spending and boundaries for the interim analysis.

For the final analysis, the log rank test will be performed using the pseudocode provided in Section 6.1. The following pseudocode can be used to compute the bounds for the final analyses and compare to the calculated log-rank statistic. The Boundaries dataset will contain the updated boundaries calculated from the interim analyses using the actual information levels observed at the interim analysis.

```

data Params_LogR;
  set logrankp(rename=(Statistic=Estimate));
  if Variable='TreatmentVariable';
  _Scale_='Score';
  _Stage_= AnalysisNumber;
  keep Variable _Scale_ _Stage_ StdErr Estimate;
run;

proc seqtest Boundary=Boundaries

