8.1.2. Supplemental and Sensitivity Analyses

For all supplemental and sensitivity analyses of the primary outcome, p-values may or may not be reported, and 95% confidence levels will be used for confidence interval estimates.

The primary analysis will be repeated in the As Treated analysis population where subjects who are not treated will be censored at enrollment. The tabular and graphical summaries described in the previous section will be replicated for this As Treated analysis.

Sensitivity analyses will be performed using Cox proportional hazards models to estimate the hazard ratio. First, an ITT analysis will be performed in which subjects who die prior to recovering are treated as experiencing a competing risk in the Fine-Gray proportional hazards regression model. Second, a Cox model will be fit with binary indicators for treatment group and disease severity Moderate vs. Severe [separate models for randomized stratum and actual stratum] as well as a treatment * disease severity interaction term. The models will be fit to the ITT analysis population. The treatment group hazard ratios and CIs will be reported for both sets of models and the interaction term p-value will be reported for the interaction models. As requested by the DSMB, a restricted mean survival time analysis will be performed as an exploratory analysis. The restricted mean recovery time estimates will be provided for each treatment group and randomized disease severity stratum as well as the difference in restricted mean recovery time between treatment groups within each of the severity strata (Table 18). Time to recovery will also be explored within prior Remdesivir treatment subgroups (Any Treatment vs. No Treatment) (Table 19).

The primary analysis will also be repeated using the other subgroups defined in Section 6.4 in place of disease severity. Each subgroup will be considered separately and the tabular and graphical summaries described in the previous section will be replicated for each subgroup. The tabular summary will also include results from an analysis of time to recovery controlling for age

and duration of symptoms as continuous covariates and baseline d-dimer and CRP values as continuous covariates. A forest plot will be generated to display the overall treatment hazard ratio estimate and CI from each of the within-stratum analyses (Table 20 and Table 21). These analyses will be performed in the ITT and As Treated populations.

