The “Disease Severity” and “Analysis Population” columns will be removed. A “Subgroup” column will be inserted to the left of the “Treatment Group” column. These tables will not display the “Any...” rows. For the analysis controlling for age, symptom duration, d-dimer, and CRP values as continuous covariates, the elements for the “Subgroup” column will state “Baseline Predictors as Continuous Covariates”. The elements for the “n” and “Median Time to Recovery” columns will display “-“. P-values will not be included in these tables.

Programming Notes for Tables 22 and 23:

P-values will not be included in these tables.

Table 22 will include a column to the left of the “n” column titled “m”. The corresponding footnote will read “m = Number of subjects readmitted for COVID-19.” Table 11 will include the following footnote: “In this analysis, subjects that recover and are subsequently readmitted for COVID-19 are censored at 28 days”.

Table 23 will include a column to the left of the “n” column titled “m”. The corresponding footnote will read “m = Number of subjects reporting use of the medication of interest.” For Table 12, the “Analysis Population” column will be replaced by a column labeled “Medication of Interest”. Separate models will be fit for the following categories of medications (see Section 6.4):

- Any Medication of Interest
- Hydroxychloroquine/Chloroquine
- Corticosteroids
- Anti-Inflammatory Drugs

The table will include the following footnote: “In this analysis, subjects that reported use of the specified medications of interest (Section 6.4 of the SAP) are censored at time of medication receipt.”

Table 24: Summary of Recoveries and Deaths by Day 29 – ITT Population

Grouping Variable	Subgroup	Treatment Group	Recovered		Did Not Recover		Deaths		Not Recovered or Died	
			n	%	n	%	n	%	n	%
Disease Severity	Moderate	Baricitinib + RDV (N=X)	x	x	x	x	x	x	x	x
		Placebo + RDV (N=X)	x	x	x	x	x	x	x	x
	Severe	Baricitinib + RDV (N=X)	x	x	x	x	x	x	x	x
		Placebo + RDV (N=X)	x	x	x	x	x	x	x	x
	Any Severity	Baricitinib + RDV (N=X)	x	x	x	x	x	x	x	x
		Placebo + RDV (N=X)	x	x	x	x	x	x	x	x
Repeat for duration of symptoms categories in Section 6.4										
N= Number of subjects in the ITT Population.										

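### The region analysis that the SAP uses to account for site drops disease severity, and the table shell removes its pooled estimate, so no planned overall recovery estimate keeps severity and also accounts for location

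*SAP*

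**What the plan says.** SAP 4.2.3 randomises 1:1 "with stratification by site and disease severity by ordinal scale", and SAP 4.2 expects subjects to be "enrolled at up to approximately 100 clinical trial sites globally". For the primary log-rank test in SAP 8.1.1, "Stratification is based on moderate versus severe disease at baseline". Site and region do not enter that test.

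SAP 6.7 pools the data over sites and then states: "Secondary analyses of the primary outcome will account for site via stratification by geographic region as noted in Section 6.4". SAP 6.4 lists region among the subgroups, once as US against non-US and once as "North American sites; Asian sites; European sites". SAP 8.1.2 gives the method: "The primary analysis will also be repeated using the other subgroups defined in Section 6.4 in place of disease severity". It continues: "Each subgroup will be considered separately and the tabular and graphical summaries described in the previous section will be replicated for each subgroup".

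Tables 20 and 21 take the layout of Table 15. In that layout the pooled row carries the hazard ratio from the stratified Cox model. The programming note for Tables 20 and 21 says: "These tables will not display the “Any...” rows". It also leaves out p-values.

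Two other checks concern location. SAP 6.7 and 8.1.2 plan a leave-one-site-out forest plot (Figure 13). Protocol Appendix B 9.4.7 plans interaction tests over subgroups that include geographic region.

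**The concern.** An analysis offered as the one that accounts for site should add location to the factors already in the primary analysis. Here region takes the place of severity. The result then differs from the primary analysis in two respects at once: location is added and a prognostic randomisation factor is removed.

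Hazard ratios are not collapsible, so leaving out a prognostic factor pulls the estimate towards 1 even when nothing is confounded. A reader who sees a smaller ratio under region stratification could conclude that the effect weakens once place of treatment is considered, when the shift comes from dropping severity. The same applies to every region-specific and other subgroup hazard ratio computed without severity as a stratifier.

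There is also a conflict inside the SAP. The body text promises that the 8.1.1 summaries, including the stratified hazard ratio, will be repeated for each subgroup variable. The shell note removes the row where that ratio would stand.

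**Working it through.** **1. The plan's sizing figure.** SAP 5 uses E = 4(1.96 + z)²/(ln θ)². With θ = 1.25 and z = 1.0364 for 85% power, E = 4 × 2.9964²/0.22314² = 35.91/0.04979 = 721.3, or 722 after rounding up. The plan's 723 agrees, and 723/0.70 = 1032.9 matches its 1032. Neither figure depends on site.

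**2. Tracing the recovery outputs for a location term.**

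| Output | Stratifier or covariates | Location? |
|---|---|---|
| Table 15 | severity | no |
| Table 16 | Fine-Gray; age, symptom duration, d-dimer, CRP; severity interaction | no |
| Table 17 | baseline ordinal score | no |
| Table 18 | restricted mean time by severity | no |
| Table 19 | prior remdesivir | no |
| Tables 20–21, region rows | within region, no severity, pooled row removed | by region only |
| Tables 22–23 | severity; readmission or medication censoring | no |
| Figures 2–9 | overall, severity, baseline score | no |
| Figure 13 | primary analysis repeated without one site at a time | site influence, no adjustment |

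If the shell governs, there is no pooled region-stratified estimate. If the 8.1.2 text governs, there is one, with severity dropped. Neither gives a pooled estimate with both.

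**3. Size, by simulation.** The documents give no severity mix, stratum recovery rates or between-site variation. These inputs are assumptions and the results are illustrative.

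*Set A.* N = 1033, one third severe, severe recovery rate one fifth to one third of moderate, three regions with rate multipliers 0.5 to 1.0, true ratio 1.25, 400 to 700 trials per setting.

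| Stratified by | Mean ratio | Power | Log-rank information V |
|---|---|---|---|
| severity | 1.22–1.24 | 84–85% | about 190 |
| region in place of severity | 1.19–1.20 | 70–79% | – |
| severity × region | 1.23–1.24 | 85–87% | about 189 |
| severity × site (about 70 sites) | – | – | about 163 |

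Information lost is (190 − 189)/190 = 0.5% for six cells and (190 − 163)/190 = 14% for severity × site.

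*Set B.* N = 1032, 70 sites, 32% severe, three regions, blocks of 2 or 4, true ratio 1.25 for power, 500 trials per cell (Monte Carlo error about 1 to 2 points). Entries are power / type I error.

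| Site SD, region SD (log hazard) | Severity | Region instead | Severity × region | Severity × site |
|---|---|---|---|---|
| 0, 0 | 0.88 / 0.044 | 0.77 / 0.024 | 0.88 / 0.044 | 0.86 / 0.050 |
| 0.3, 0.2 | 0.90 / 0.030 | 0.82 / 0.020 | 0.91 / 0.032 | 0.89 / 0.036 |
| 0.6, 0.3 | 0.79 / 0.024 | 0.72 / 0.008 | 0.80 / 0.024 | 0.85 / 0.040 |
| 0.9, 0.3 | 0.69 / 0.018 | 0.64 / 0.014 | 0.70 / 0.022 | 0.85 / 0.064 |

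In the same four rows the estimated ratio fell from 1.261 to 1.209, 1.251 to 1.208, 1.210 to 1.185 and 1.187 to 1.176 when region replaced severity. On the log scale these are drops of 0.042, 0.035, 0.021 and 0.009.

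**4. Scale.** The standard error of the log ratio at 723 recoveries is about 2/√723 = 0.074. The drop is therefore roughly one eighth (0.009/0.074) to just over one half (0.042/0.074) of a standard error.

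**The case against.** The strongest reply is that the promised analysis is there. Section 6.4 treats region as a subgroup, and SAP 8.2 uses the word stratified for estimates shown in separate rows. On that reading the region rows of Tables 20 and 21 and the forest plots are what 6.7 meant. This is a fair reading of 6.7, but those rows still omit severity and give no overall estimate.

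A reader might infer that no overall recovery effect reflecting location will be reported at all. The documents do not support that. The 8.1.2 text promises replicated summaries and a forest plot of an overall hazard ratio, though its wording could mean the pooled or the within-region value. The Figure 10 mock-up is not visible in the text available, and SAP 17 allows added summaries. Leave-one-site-out tests the influence of single sites, and the protocol's interaction tests cover region. These are partial checks, because neither yields a location-adjusted overall effect.

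A reader might also infer that omitting a randomisation stratum undermines the primary test. It does not: in Set B the planned test was conservative, with type I error from 0.044 down to 0.018.

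Two further points stand. The power figures describe an analysis whose tables carry no p-values, so they serve only as an index of precision. And severity × region gains little over severity alone (0.70 against 0.69 at the strongest site variation), because two or three regions are a coarse stand-in for up to about 100 sites. The case for the change is interpretability at almost no cost, more than efficiency.

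**Conclusion.** The point holds as a defect in secondary analyses. The region analysis discards a randomisation stratum, the shell note conflicts with the body text, and under either text no planned overall estimate keeps severity while accounting for location. The subgroup hazard ratios share the omission.

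The effect is modest: a drop of about 0.01 to 0.04 in the log ratio across the two sets of simulations. It is small beside a standard error of 0.074. However, both estimates come from the same patients and the shift has a consistent direction, so it could be misread as a location effect. Its size rests on assumed severity mix, recovery rates and site variation; the direction was the same in every setting tried.

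The primary conclusion, its type I error and the sample size are unaffected. The finding covers this SAP and the protocol; the manufacturer's addendum mentioned in SAP 2.1 is not part of the documents.

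**What to change.** Leave the primary test unchanged. Then:

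- In SAP 6.7 and 8.1.2, define the location analysis as the log-rank test and Cox model stratified by severity × region (North America, Asia, Europe). Report its pooled hazard ratio and confidence interval as one sensitivity row beside Table 15.
- For Tables 20 and 21, replace the substitution of the subgroup variable for severity with stratification by severity within each subgroup, except for the severity subgroups themselves.
- Align the Tables 20 and 21 note with the 8.1.2 text, so that both say the same about the pooled row and about what the forest plot shows.
- State in 6.7 that region is only a coarse proxy for up to about 100 sites, so that the row is not read as full adjustment for site.

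The cost is SAP wording and one model row. Six strata lose about 0.5% of the log-rank information in Set A. Full severity × site stratification is not proposed: it lost about 14% there, although it held power better in Set B when site variation was strong.

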6.8. Multiple Comparisons/Multiplicity

There is only one primary outcome measure. The study utilizes a group-sequential design to control the overall type I error rate while allowing for formal interim analyses of the primary outcome measure (as described in Section 6.6 and Section 8.1). There is no planned adjustment for multiple comparisons in any secondary or exploratory analyses.

7. STUDY SUBJECTS

7.1. Disposition of Subjects

A summary of the reasons that subjects were screened but not enrolled will be tabulated (Table 1).

The composition of analysis populations, including reasons for subject exclusion will be summarized by treatment group and disease severity (Table 2). A subject listing of analysis population eligibilities will be generated (Listing 1).

The disposition of subjects will be tabulated by treatment group and disease severity (Table 3). Study milestones included in the table will include, but not limited to: the total number of subjects that were randomized, completed expected blood draws, completed Study Day 15 visit, completed Study Day 22 visit, and completed Study Day 29 visit. For the calculation of percentages, subjects who die will not be included in the denominators for visits/assessments beyond their death.

Treatment compliance will be summarized by treatment group (Table 4). Summaries of prior Remdesivir treatment by treatment group will also be provided (Table 5 and Table 6)

A flowchart showing the disposition of study subjects, adapted from the Consort Statement [4] will be generated (Figure 1). This figure will present the number of subjects screened, randomized, lost to follow-up, and analyzed, by treatment group and disease severity.

A listing of subjects who discontinued dosing or terminated study follow-up and the reason will be generated (Listing 2).

